4.1 Example of the BLRM Using BMS-986242 Monotherapy Dose Escalation

According to safety consideration and clinical judgement, dose level 25 mg is recommended as the starting dose for BMS-986242 monotherapy. With the current BMS-986242 prior specified in the Section 1.2.1 the following flow chart illustrates possible scenarios (the model's recommendations) after dose level 25mg using available DLT information in Figure 3.

Figure 3: Hypothetical Scenarios for BMS-986242 Dose Escalation After Dose Level 25mg Based on BLRM (-Copula) Model

Note: It is assumed that patient does not get combination treatment in case there is a mono DLT

[REDACTED]

[REDACTED]

[REDACTED]

[REDACTED]

█ [REDACTED]

APPENDIX 8 CYP3A AND CYP2B6 GUIDANCE

The lists below are not meant to be all inclusive. Please consult individual drug labels for further information. Additional information is also available at:

<http://www.fda.gov/Drugs/DevelopmentApprovalProcess/DevelopmentResources/DrugInteractionsLabeling/ucm093664.htm>

Table 1: Classification of In Vivo Inhibitors of CYP Enzymes

CYP Enzymes	Strong Inhibitors ^a ≥ 5-fold Increase in AUC or > 80% Decrease in CL	Moderate Inhibitors ^b ≥ 2 but < 5-fold Increase in AUC or 50-80% Decrease in CL	Weak Inhibitors ^c ≥ 1.25 but < 2-fold Increase in AUC or 20-50% Decrease in CL
CYP3A	Boceprevir, clarithromycin, conivaptan, grapefruit juice, ^d indinavir, itraconazole, ketoconazole, lopinavir/ritonavir, mibefradil, ^e nefazodone, nelfinavir, posaconazole, ritonavir, saquinavir, telaprevir, telithromycin, voriconazole	Amprenavir, aprepitant, atazanavir, ciprofloxacin, darunavir/ritonavir, diltiazem, erythromycin, fluconazole, fosamprenavir, grapefruit juice, ^d imatinib, verapamil	Alprazolam, amiodarone, amlodipine, atorvastatin, bicalutamide, cilostazol, cimetidine, cyclosporine, fluoxetine, fluvoxamine, ginkgo, ^f goldenseal, ^f isoniazid, nilotinib, oral contraceptives, ranitidine, ranolazine, tipranavir/ritonavir, zileuton

Please note that this is not an exhaustive list.

^a A strong inhibitor for a specific CYP is defined as an inhibitor that increases the AUC of a sensitive substrate for that CYP by equal to or more than 5-fold.

^b A moderate inhibitor for a specific CYP is defined as an inhibitor that increases the AUC of a sensitive substrate for that CYP by less than 5-fold but equal to or more than 2-fold.

^c A weak inhibitor for a specific CYP is defined as an inhibitor that increases the AUC of a sensitive substrate for that CYP by less than 2-fold but equal to or more than 1.25-fold.

^d The effect of grapefruit juice varies widely among brands and is concentration, dose, and preparation dependent. Studies have shown that it can be classified as a “strong CYP3A inhibitor” when a certain preparation was used (eg, high dose, double strength) or as a “moderate CYP3A inhibitor” when another preparation was used (eg, low dose, single strength).

^e Withdrawn from the United States market because of safety reasons.

^f Herbal product.

Abbreviations: AUC = area under the concentration-time curve; CL = clearance; CYP = cytochrome P450.

Table 2: Classification of In Vivo Inducers of CYP Enzymes

CYP Enzymes	Strong Inducers ≥ 80% Decrease in AUC	Moderate Inducers 50-80% Decrease in AUC	Weak Inducers 20-50% Decrease in AUC
CYP3A	Avasimibe, ^a carbamazepine, phenytoin, rifampin, St. John's wort ^b	Bosentan, efavirenz, etravirine, modafinil, nafcillin	Amprenavir, aprepitant, armodafinil, echinacea, ^c pioglitazone, prednisone, rufinamide

Please note that this is not an exhaustive list.

^a Not a marketed drug.

^b The effect of St. John's wort varies widely and is preparation dependent.

^c Herbal product.

Abbreviations: AUC = area under the concentration-time curve; CYP = cytochrome P450.

Table 3: Examples of Sensitive In Vivo CYP Substrates and CYP Substrates with Narrow Therapeutic Range

CYP Enzymes	Sensitive Substrates ^a	Substrates with Narrow Therapeutic Range ^b
CYP3A	Alfentanil, aprepitant, budesonide, buspirone, conivaptan, darifenacin, darunavir, dasatinib, dronedarone, eletriptan, eplerenone, everolimus, felodipine, indinavir, fluticasone, lopinavir, lovastatin, lurasidone, maraviroc, midazolam, nisoldipine, quetiapine, saquinavir, sildenafil, simvastatin, sirolimus, tolvaptan, tipranavir, triazolam, vardenafil	Alfentanil, astemizole, ^c cisapride, ^c cyclosporine, dihydroergotamine, ergotamine, fentanyl, pimozone, quinidine, sirolimus, tacrolimus, terfenadine ^c
CYP2B6	Bupropion, efavirenz	

Please note that this is not an exhaustive list.

^a Sensitive CYP substrates refers to drugs whose plasma AUC values have been shown to increase 5-fold or higher when co-administered with a known CYP inhibitor.

^b CYP substrates with narrow therapeutic range refers to drugs whose exposure-response relationship indicates that small increases in their exposure levels by the concomitant use of CYP inhibitors may lead to serious safety concerns (eg, Torsades de Pointes).

^c Withdrawn from the United States market because of safety reasons.

Abbreviations: AUC = area under the concentration-time curve; CYP = cytochrome P450.

APPENDIX 9 MANAGEMENT ALGORITHMS FOR IMMUNO-ONCOLOGY AGENTS

These general guidelines constitute guidance to the Investigator and may be supplemented by discussions with the Medical Monitor representing the Sponsor. The guidance applies to all immuno-oncology (I-O) agents and regimens.

A general principle is that differential diagnoses should be diligently evaluated according to standard medical practice. Non-inflammatory etiologies should be considered and appropriately treated.

Corticosteroids are a primary therapy for I-O drug-related adverse events. The oral equivalent of the recommended intravenous doses may be considered for ambulatory patients with low-grade toxicity. The lower bioavailability of oral corticosteroids should be taken into account when switching to the equivalent dose of oral corticosteroids.

[figure not shown]
Consultation with a medical or surgical specialist, especially prior to an invasive diagnostic or therapeutic procedure, is recommended.

The frequency and severity of the related adverse events covered by these algorithms will depend on the I-O agent or regimen being used.

Updated: 05-Jul-2016

GI Adverse Event Management Algorithm

Rule out non-inflammatory causes. If non-inflammatory cause is identified, treat accordingly and continue I-O therapy. Opiates/narcotics may mask symptoms of perforation. Infliximab should not be used in cases of perforation or sepsis.

[figure not shown]

Patients on IV steroids may be switched to an equivalent dose of oral corticosteroids (e.g. prednisone) at start of tapering or earlier, once sustained clinical improvement is observed. Lower bioavailability of oral corticosteroids should be taken into account when switching to the equivalent dose of oral corticosteroids.

Updated 05-Jul-2016

Renal Adverse Event Management Algorithm

Rule out non-inflammatory causes. If non-inflammatory cause, treat accordingly and continue I-O therapy

[figure not shown]

Patients on IV steroids may be switched to an equivalent dose of oral corticosteroids (e.g. prednisone) at start of tapering or earlier, once sustained clinical improvement is observed. Lower bioavailability of oral corticosteroids should be taken into account when switching to the equivalent dose of oral corticosteroids.

Updated 05-Jul-2016

Pulmonary Adverse Event Management Algorithm

Rule out non-inflammatory causes. If non-inflammatory cause, treat accordingly and continue I-O therapy. Evaluate with imaging and pulmonary consultation.

[figure not shown]

Patients on IV steroids may be switched to an equivalent dose of oral corticosteroids (e.g. prednisone) at start of tapering or earlier, once sustained clinical improvement is observed. Lower bioavailability of oral corticosteroids should be taken into account when switching to the equivalent dose of oral corticosteroids.

Updated 05-Jul-2016

Hepatic Adverse Event Management Algorithm

Rule out non-inflammatory causes. If non-inflammatory cause, treat accordingly and continue I-O therapy. Consider imaging for obstruction.

Patients on IV steroids may be switched to an equivalent dose of oral corticosteroids (e.g. prednisone) at start of tapering or earlier, once sustained clinical improvement is observed. Lower bioavailability of oral corticosteroids should be taken into account when switching to the equivalent dose of oral corticosteroids.

[figure not shown]
*I-O therapy may be delayed rather than discontinued if AST/ALT ≤ 8 x ULN or T.bili ≤ 5 x ULN.

**The recommended starting dose for grade 4 hepatitis is 2 mg/kg/day methylprednisolone IV.

Updated 05-Jul-2016

Endocrinopathy Management Algorithm

Rule out non-inflammatory causes. If non-inflammatory cause, treat accordingly and continue I-O therapy. Consider visual field testing, endocrinology consultation, and imaging.

[figure not shown]

Patients on IV steroids may be switched to an equivalent dose of oral corticosteroids (e.g. prednisone) at start of tapering or earlier, once sustained clinical improvement is observed. Lower bioavailability of oral corticosteroids should be taken into account when switching to the equivalent dose of oral corticosteroids.

Updated 05-Jul-2016

Skin Adverse Event Management Algorithm

Rule out non-inflammatory causes. If non-inflammatory cause, treat accordingly and continue I-O therapy.

Patients on IV steroids may be switched to an equivalent dose of oral corticosteroids (e.g. prednisone) at start of tapering or earlier, once sustained clinical improvement is observed. Lower bioavailability of oral corticosteroids should be taken into account when switching to the equivalent dose of oral corticosteroids.

[figure not shown]
*Refer to NCI CTCAE v4 for term-specific grading criteria.

^If SJS/TEN is suspected, withhold I-O therapy and refer patient for specialized care for assessment and treatment. If SJS or TEN is diagnosed, permanently discontinue I-O therapy.

Updated 05-Jul-2016

Neurological Adverse Event Management Algorithm

Rule out non-inflammatory causes. If non-inflammatory cause, treat accordingly and continue I-O therapy.

Patients on IV steroids may be switched to an equivalent dose of oral corticosteroids (e.g. prednisone) at start of tapering or earlier, once sustained clinical improvement is observed. Lower bioavailability of oral corticosteroids should be taken into account when switching to the equivalent dose of oral corticosteroids.

Updated 05-Jul-2016

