investigators that it is in the best interest of the participant to receive additional treatment with BMS-986242 and nivolumab (eg, if the participant has demonstrated a response to treatment).

- During the DLT evaluation period, if a participant receives dose reduction and experiences a DLT at the lower dose, this DLT will be attributed to the highest dose level administered.
- For data collection and analysis purposes, all participants will continue to be classified by the original treatment arm.

Table 7.4.2-1: Dose Modifications

Dose Modification Criteria for Study Treatment-Related Adverse Events	BMS-986242 Monotherapy Modification at the Next Dose	BMS-986242 Combination Modification at the Next Dose
QTcF > 500 msec confirmed by at least 1 repeat ECG and at least 60 msec above baseline	Interrupt if needed to optimize electrolyte management. If event persists after electrolyte optimization (including dose modification of BMS-986242, if necessary), discontinue. Participants may proceed to get nivolumab monotherapy.	Interrupt if needed to optimize electrolyte management. If event persists after electrolyte optimization (including dose modification of BMS-986242, if necessary), discontinue. However, treatment with nivolumab may continue after discussion between PI and Medical Monitor.
Any other study treatment-related \geq Grade 3 adverse event that does not meet permanent discontinuation criteria (Section 8)	Decrease 1 level of BMS-986242 (no lower than 25 mg).	Decrease 1 level of BMS-986242 (no lower than 25 mg) in combination with same dose of nivolumab.
Grade 2 LFT abnormalities that do not resolve within 1 week	Interruption of BMS-986242 Continuation of BMS-986242 at a lower dose level may be considered after discussion with the Study Director/Medical Monitor. Participants may proceed to get nivolumab monotherapy.	NA
Grade 2 LFT abnormalities that resolve in 1 week	Interrupt dosing until improvement to Grade 1 or baseline and resume at same dose. If recurrence of Grade 2 LFT elevations, decrease 1 level.	NA

Abbreviations: LFT = liver function test; QTcF = QT interval corrected for heart rate using Fridericia’s formula; NA = not applicable; PI = principal investigator.

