7.4.4 Criteria to Resume Treatment

Participants experiencing AEs not meeting criteria for permanent discontinuation as outlined in [Section 8.1](#) and [Section 8.2](#) may resume treatment with study treatment under the following criteria:

- Participants may resume treatment with study treatment when the study treatment-related AE(s) resolves to Grade ≤ 1 or baseline value with the following EXCEPTIONS:
 - Participants may resume treatment in the presence of Grade 2 fatigue.
 - Participants who have not experienced a Grade 3 study treatment-related skin AE may resume treatment in the presence of Grade 2 skin toxicity.
- Participants with Grade 2 uveitis or eye pain or blurred vision not meeting DLT criteria ([Section 7.4.1](#)) must resolve to baseline prior to resuming study treatment.
- Study treatment-related pulmonary toxicity, diarrhea, or colitis must have resolved to baseline before treatment is resumed.
- Participants with study treatment-related endocrinopathies adequately controlled with only physiologic hormone replacement may resume treatment.
- If the criteria to resume treatment are met, the participant should restart treatment at the next scheduled time point per protocol.
- The consideration to re-initiate study treatment under these exceptions will be made on a case-by-case basis after considering the overall benefit/risk profile and in consultation between the investigator and the study Sponsor. Any AE with clinical risk will be assessed on a case-by-case basis with the investigator and the BMS Medical Monitor to determine the risks and benefits of continuing on study treatment following resolution versus discontinuing study treatment permanently.
- If treatment with study treatment is delayed > 6 weeks, the participant must be permanently discontinued from study treatment, except as specified in [Section 7.4.2](#).

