7.4.5 Guidelines for Permanent Discontinuation Secondary to Adverse Events

Participants will be required to permanently discontinue both study treatments for the following AEs:

- Clinical deterioration, as assessed by the investigator
- Grade 3 infusion reaction that does not return to Grade 1 in less than 6 hours
- Grade 3 pneumonitis, bronchospasm, neurologic toxicity, uveitis, or myocarditis
- Life-threatening skin toxicity (toxic epidermal necrolysis)

- Any Grade 4 AE; however, an exception may be made for the following upon consultation between the investigator and BMS Medical Monitor:
 - Grade 4 electrolyte abnormalities < 72 hours in duration
 - Grade 4 neutropenia < 7 days in duration
 - Grade 4 lymphopenia
 - Grade 4 increase in amylase or lipase that is not associated with clinical or radiographic evidence of pancreatitis
- Abnormal liver function tests meeting criteria for a potential DILI.
- Any dosing delay lasting > 6 weeks will be cause for permanent discontinuation. Extensions to the period of dose delays may be granted for individual participants on a case-by-case basis after specific consultation and agreement between the investigator and BMS Medical Monitor in settings where benefit/risk may justify continued study treatment (eg, participant deriving clinical benefit who requires prolonged steroid taper for management of non-DLT immune-related AEs or experiences delays for management of a non-treatment-related AE).
- Accordingly, dosing delays to allow for prolonged steroid tapers to manage study treatment-related AEs are allowed. Additionally, dosing delays > 6 weeks that occur for non-treatment-related reasons may be allowed if approved by the BMS Medical Monitor.
- The consideration to re-initiate study treatment under these exceptions will be made on a case-by-case basis after considering the overall benefit/risk profile and in consultation between the investigator and the Sponsor.
- Prior to re-initiating treatment in a participant with a dosing delay lasting > 6 weeks, the BMS Medical Monitor must be consulted.
- Tumor assessments should continue per protocol even if dosing is delayed.

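### Appendix 9 calls for a permanent stop on any diagnosis of SJS or TEN, but the mandatory stop list in Section 7.4.5 names only TEN and Grade 4 events (minor)

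*Combined protocol and SAP*

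**What the plan says.** Two parts of the combined protocol and SAP deal with stopping treatment after a severe skin reaction.

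- **Appendix 9, skin algorithm footnote.** I-O therapy is withheld when SJS or TEN is suspected, and then: "If SJS or TEN is diagnosed, permanently discontinue I-O therapy". Diagnosis is the trigger and no grade is given. The appendix describes itself as guidance to the investigator and says that it covers all I-O agents and regimens.
- **Section 7.4.5.** This is the list of events for which both study treatments must be stopped permanently. Its only skin-specific entry is "Life-threatening skin toxicity (toxic epidermal necrolysis"). Its grade-based entry is "Any Grade 4 AE; however, an exception may be made for the following upon consultation between the investigator and BMS Medical Monitor". Its Grade 3 entries are an infusion reaction that is slow to resolve, and "Grade 3 pneumonitis, bronchospasm, neurologic toxicity, uveitis, or myocarditis".

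For related events of Grade 3 or higher that do not meet the permanent-stop criteria, the combination column of Table 7.4.2-1 (Section 7.4.2) says: "Decrease 1 level of BMS-986242 (no lower than 25 mg) in combination with same dose of nivolumab". On restarting, Section 7.4.4 says "Participants may resume treatment with study treatment when the study treatment-related AE(s) resolves to Grade" 1 or lower, or to the baseline value. It adds one skin-specific allowance: "Participants who have not experienced a Grade 3 study treatment-related skin AE may resume treatment in the presence of Grade 2 skin toxicity".

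**The concern.** The unconditional instruction for SJS sits in an appendix labelled as guidance, while the list that binds sites leaves SJS out. A coordinator working through Sections 7.4.2 to 7.4.5 and 8.1 could reach a different action from one who reads the Appendix 9 footnote. At stake is possible re-exposure to nivolumab plus a first-in-human agent after a severe skin reaction for which the sponsor's own guidance is to stop for good.

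**Working it through.** No arithmetic applies. The check follows each type of case through the text.

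1. **TEN.** Named in Appendix 9 and in Section 7.4.5. Consistent.
2. **Grade 4 SJS.** A stop in Appendix 9 by diagnosis, and in Section 7.4.5 through the Grade 4 entry. The four exceptions to that entry (electrolytes, neutropenia, lymphopenia, amylase or lipase) include no skin event. Consistent.
3. **SJS below Grade 4.** A stop in Appendix 9. In Section 7.4.5, none of the six Grade 3 toxicities is dermatologic: infusion reaction, pneumonitis, bronchospasm, neurologic toxicity, uveitis, myocarditis. If the skin bullet is read broadly, with TEN as an example only, it picks up life-threatening SJS but not the rest. Not consistent.

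A treatment-related Grade 3 SJS during combination treatment then runs as follows:

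- **Is another stop triggered?** Section 7.4.5 also stops for clinical deterioration as judged by the investigator and, subject to agreed extensions, for a dosing delay over 6 weeks. Section 8.1 stops when the investigator judges that continuing is not in the participant's interest. Any of these may end treatment in a given case. None depends on the SJS diagnosis.
- **If none applies,** Section 8.1 refers to Section 7.4.5 for protocol-defined stops, and SJS is not there. The Table 7.4.2-1 row applies. Under Section 7.4.2 both drugs are first interrupted until Grade 1 or baseline. BMS-986242 then drops one level and nivolumab resumes at the same dose.
- **Does Section 7.4.4 block the restart?** No. Its Grade 2 skin allowance is closed to someone who has had a related Grade 3 skin event, so recovery to Grade 1 or baseline is needed. After that, SJS is not excluded.
- **Do the DLT rules close the gap?** No. The general Grade 3 criterion in Section 7.4.1.1 leaves out dermatologic toxicity, and the dermatologic criteria concern rash. Where a DLT is declared for another reason, such as more than 2 weeks of delay, Section 7.4.3 requires treatment to be held, not ended.
- **Does the body text send skin events to Appendix 9?** Section 7.4.3 sends Grade 2 hepatic, pulmonary, renal, gastrointestinal and neurological events there. Skin is not in that list. Section 7.4.1 cites Section 7.7.1.4 for the algorithms, but that section is not visible in the public text.

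In the Part 1 lead-in, Section 7.4.1 already bars entry to the combination after an immune-related event of Grade 2 or higher attributed to BMS-986242, apart from thyroid events. The gap therefore mainly concerns combination treatment.

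A separate editorial check: Section 7.4.3 points to Section 8.2 for the participants who must stop permanently, and Section 7.4.4 cites Sections 8.1 and 8.2 for the criteria. Section 8.2 covers withdrawal of consent and follow-up and lists no adverse events.

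**The case against.** The strongest reply is that the protocol already contains the instruction. Appendix 9 is part of it, its footnote is explicit, and a specific rule for a diagnosed condition would ordinarily prevail over silence in a general list. Section 7.4.4 permits resumption but does not direct it, and says that "Any AE with clinical risk will be assessed on a case-by-case basis with the investigator and the BMS Medical Monitor". Section 9 requires immediate safety concerns to be discussed with the Sponsor at once, and Section 7.4.2 calls its criteria general guidelines and allows more conservative action. Section 7.7.1.4 may require the algorithms to be followed, in which case the stop is already binding whatever Section 7.4.5 lists. The gap also needs SJS to be gradable below 4, and the documents cite CTCAE without reproducing it.

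Most of this stands, and it sets the severity. It does not remove the mismatch: the section headed as the required-stop list omits a diagnosis that the appendix treats as an absolute stop, and the visible safeguards in the body text are discretionary.

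A reader might infer that the protocol authorises rechallenge after SJS, or that nivolumab simply continues. The documents do not support either reading. The first requires Section 7 to be read without Appendix 9. The second overlooks the interruption of both drugs in Section 7.4.2.

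**Conclusion.** The concern holds as a minor inconsistency between body text and appendix on a safety rule. It is confined to diagnosed, treatment-related SJS below Grade 4 that triggers no other stop, mainly during combination treatment, among up to 298 participants. The documents give no rate; cases would be few. TEN and Grade 4 SJS are handled consistently.

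The conclusion rests on one assumption, that SJS can be graded below 4. If it were always Grade 4, the Grade 4 entry would close the gap. One point cannot be settled: whether Section 7.7.1.4 makes Appendix 9 binding. If it does, the stop is already required, and what remains is that Section 7.4.5 does not repeat it. Dose finding, endpoints and analysis are not affected. The Section 8.2 pointers are an editorial matter and add no weight to the SJS point.

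**What to change.** Change the skin bullet in Section 7.4.5 to: *Stevens-Johnson syndrome (any grade), toxic epidermal necrolysis, or other life-threatening skin toxicity*. This matches the Appendix 9 footnote, which sets neither a grade nor a relatedness condition, and it removes the dependence on how SJS is graded.

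Editorial only: in Sections 7.4.3 and 7.4.4, replace the pointer to Section 8.2 with Section 7.4.5. Keep Section 8.1 in Section 7.4.4, because it carries the investigator-judgement grounds for stopping.

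The cost is one bullet and two cross-references in the next amendment, with no change to design, sample size, assessments or analysis.
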